## 2.4. Screening and enrollment

Patients being evaluated in the emergency room, outpatient clinics, other urgent/emergent care settings, or admitted to the hospital with COVID-19 will be screened for eligibility. We will also consider interested participants who reach out to us as a result of advertisements or other outreach efforts. Inclusion and exclusion criteria will be reviewed to ensure participant suitability. After participant eligibility is confirmed, informed consent will be obtained from study participants using documents and processes approved by the respective Institutional Review Board (IRB)/Ethics Committee. Specific consent mechanisms and other unique aspects applied to meet regulatory requirements in a specific country are specified in **Appendix 3**. Participants will be given the opportunity to have all questions regarding their participation answered. Enrollment will be competitive (will occur across all active sites, without an enrollment cap per site) until a total of 700 patients have been recruited.

## 2.5. Randomized intervention

The randomized intervention will be: (1) fenofibrate (or its active metabolite, fenofibric acid) administered for 10 days (see **Appendix 3** for specific preparations and dosing), with appropriate dose reductions or exclusions will be implemented for patients with chronic kidney disease as per the approved preparation label; (2) Placebo of similar appearance (1:1 ratio). These interventions will be added to usual care. Participants and investigators (including research team members who administer the Dyspnea Borg scale and symptoms questionnaires) will be blinded to the randomized intervention. Primary analyses will be performed on an intent-to-treat basis.

## 2.6. Randomization procedure

Following informed consent, participants will be randomized to one of the 2 treatment arms. A stratified blocked randomization with randomly permuted blocks will be performed based on site,

sex, age group, and inpatient vs. outpatient status, given the strong impact of these factors on outcomes in COVID-19. A sufficient number of complete blocks will be generated for each stratum so that randomized assignments are available for every eligible subject. Each block will contain an equal number of allocations to each arm.

## **2.7. Participant withdrawal / Early termination**

Participants may voluntarily withdraw from the study at any time and for any reason. The reason for study discontinuation will be recorded on the source documents and in all such participants, we will document: (1) vital signs (inpatients only); (2) compliance with the treatment; (3) adverse effects. (4) specific reason for withdrawal if possible; (5) functional status and symptoms (including the dyspnea Borg scale).

The study medication will be discontinued if any of the following occur at any time: (1) acute kidney injury with eGFR<30 ml/m^2/min; (2) Suspected or confirmed rhabdomyolysis; (3) Red or brown urine, which may indicate myoglobinuria, unless considered by the investigator to be clearly not due to rhabdomyolysis (for instance, in the presence of normal circulating creatine kinase); (4) Liver failure or increased AST or ALT to >3 times the upper limit of normal. In cases in which the medication is discontinued, data collection will continue normally as per the usual study protocol.

## **2.8. Concomitant Medication**

Participants will be treated by their clinicians, at their discretion, with standard of care medications for COVID-19 and associated comorbidities. Participants will be allowed to receive antiviral, immunomodulatory, or convalescent plasma. Since fenofibrate/fenofibric acid are well-known medications, enrollment in other clinical trials will be allowed as long as fenofibrate/fenofibric acid use is not an exclusion criterion for other trials.

We will remind inpatient clinicians to consider potential interactions with fenofibrate, particularly in patients who require *de novo* warfarin treatment (which should ultimately be guided by INR checks as per standard practice). We will also ask them to try avoiding the *de novo* use of medications that may interact with fenofibrate or fenofibric acid (colchicine, glimepiride, cyclosporine, tacrolimus, statins) unless clear indications exist in the absence of suitable therapeutic alternative agents; if glimepiride, cyclosporine or tacrolimus are required, we will discontinue the study medication. For colchicine, atorvastatin and simvastatin, we will ask clinicians to be mindful of a potential interaction, which is however, not anticipated to constitute a significant risk with only 10 days of treatment (see section on “Risks to study subjects”). If cholestyramine or colestipol are part of the medical regimen at baseline or during the period of study medication administration, we will ask participants to take the study medication at least 1 hour before or 6 hours after the bile acid binding resin to avoid a pharmacokinetic interaction (reduced absorption). For outpatients, we will ask participants to contact us if any new medication is initiated by their physicians during the treatment period, and we will establish a similar approach in communication with the prescribing clinician.

## **2.9. Drug dispensing**

The drug will be dispensed by a Pharmacy within each country and/or institution, or directly by the investigators. At the University of Pennsylvania, the medication and placebo will be dispensed by the UPenn Investigational Drug Pharmacy.

## **2.10. Follow-up assessments**

For participants randomized as inpatients, daily assessments (via medical record review) will be performed to assess clinical status, with particular attention to the study endpoints (death, mechanical ventilation and the  $\text{FiO}_2/\text{SpO}_2$  ratio), until hospital discharge or 30 days (whichever is shortest). For participants discharged prior to 30 days-post randomization, a follow-up call will be performed at the ~30-day time point to assess vital and functional status, symptoms and major adverse events, including hospitalizations.

For participants randomized as outpatients or discharged within 24 hours of receiving the first dose of the study medication, participants will be called at approximately 5, 10, 15 and 30 days post-randomization, in order to assess vital and functional status, hospitalization status, the severity of dyspnea (via the modified Dyspnea Borg Scale, **Appendix 1**) and major adverse events. An effort will be made to make these assessments at the exact time points, but we recognize that this is often not possible due to work schedules and inability to get in touch with participants for various reasons. In these instances, we will make the assessments at time points that are as close as possible to the scheduled time points.

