**Figure 2. Hierarchical ranking for the primary endpoint**

= outpatient; = inpatient.

\* For participants enrolled as inpatients, inpatient mandatory data collection will occur until discharge or 30 days (whichever is shorter)

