### **8.2. Risks to study subjects**

All subjects will be adults able to give informed consent. Subjects will be enrolled regardless of sex, race or ethnicity, aiming to assure adequate representation of women and ethnic minorities. Children will not be enrolled.

The risks to study subjects are related to the potential side effects of the study intervention. The dose used in this trial is the starting dose for primary hypercholesterolemia and mixed dyslipidemia and is utilized as a chronic therapy, for months or years. We propose to administer this dose for only 10 days.

With chronic therapy, adverse reactions > 2% and at least 1% greater than placebo include abnormal liver blood tests (increased AST and ALT) increased creatine kinase (CPK), and rhinitis. Rhabdomyolysis have been reported in patients taking fenofibrate, but is considered extremely

rare, with <20 cases reported worldwide for fibrate monotherapy. Moreover, the median duration of therapy prior to rhabdomyolysis was 17.5 days. In the Fenofibrate Intervention and Event Lowering in Diabetes (FIELD) trial, 9,795 were randomized to fenofibrate or placebo for 5 years. This provided >8 million patient-days of observation in the active arm alone. In this trial, only 3 patients allocated to fenofibrate had rhabdomyolysis, which in each case fully resolved; this incidence was not significantly different than that of the placebo arm (1 case of rhabdomyolysis). The risk of rhabdomyolysis may be increased during co-administration with a statin, in renal failure, or hypothyroidism. Accordingly, we will exclude all patients with advanced renal dysfunction and those with a history of hypothyroidism.

Regarding statins, although there is an increase in reports of rhabdomyolysis with statin-fibrate combined therapy, this risk appears to be much higher when statins are combined with gemfibrozil than fenofibrate. In a meta-analysis of 6 trials including 1,628 subjects taking fenofibrate in combination with statin therapy, no case of myopathy or rhabdomyolysis was reported. This included data from the LCP-AtorFen trial, in which atorvastatin (40 mg/d) was administered alone or with fenofibrate for 12 weeks, as well as some studies with simvastatin (20 mg/d).

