
Given that we will only administer 10 days of therapy, we consider the risk of rhabdomyolysis, even in patients taking statins or colchicine, to be negligible. Nevertheless, as a precaution, we will exclude patients who are taking statins other than simvastatin and atorvastatin; similarly, we will exclude patients who are taking simvastatin or atorvastatin at doses >40 mg/d,

since doses >40 mg/d of these 2 drugs in combination with fenofibrate have not been specifically studied. Finally, we will ask site investigators to communicate any occurrence of rhabdomyolysis to the Principal Investigator, who in turn will immediately communicate them to the DSMB for a formal assessment (with unblinding of the DSMB if required). We will inquire about potential manifestations of rhabdomyolysis (particularly hemoglobinuria) in all data collection forms and the study medication will be discontinued immediately upon suspected or confirmed rhabdomyolysis.

Fenofibrate can increase serum transaminases and/or serum creatinine and periodic monitoring is recommended during chronic therapy. However, we will only utilize it for 10 days in this trial and will exclude patients with active liver disease or advanced renal disease. Therefore, the need for periodic monitoring does not apply for such as short treatment. Moreover, the mild increase in serum creatinine is not thought to be due to impaired true glomerular function, as measured by inulin clearance, the gold standard measure of renal function. This creatinine rise does not increase the risk of adverse renal outcomes or cardiovascular events, and is fully reversible upon discontinuation.

Fenofibrate increases cholesterol excretion into the bile, leading to risk of cholelithiasis. This is not anticipated to be a problem with 10 days of therapy, and our trial will exclude patients with a history of gallbladder disease. As recommended by the approved prescribing information, we will also exclude nursing mothers, and patients with known hypersensitivity to fenofibrate or fenofibric acid.

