### UNITED STATES:

#### *Fenofibrate preparation and dosing*

In the US, the drug and placebo will be prepared (encapsulated) by the Penn Investigational Drug Pharmacy. It will be shipped to IDS services in other enrollment sites. Administration will be double-blinded (Investigators and patient).

We will utilize Tricor tablets. The dose will be 145 mg/day with appropriate dose correction for patients with chronic kidney disease (CKD). The daily dose of Tricor for patients with CKD stage 2 will be 96 mg/d and the dose for CKD stage 3 will be 48 mg/d. In all cases, the intended duration of randomized treatment will be for 10 days.

The medication will be administered by mouth regardless of meals; in patients who are intubated, we will administer the crushed tablet (or placebo) via nasogastric tube. The latter procedure requires opening the capsule and therefore unblinds the administering nurse, which is acceptable, since in that setting (once the patient is intubated), subjective endpoints do not influence the study primary (only time to death and days of mechanical ventilation do, in tiers 1 and 2). The same is true for all secondary outcomes. Moreover, the patient and investigator will remain blinded. We have considered the alternative of preparing a blinded solution of active medication vs. placebo by IDS to be sent to the floor for administration via NG tube; however, we lack reliable data regarding the stability of the medication in solution at ambient temperature for various periods of time. Therefore, we have opted against this option.

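### Inpatients discharged more than 24 hours after the first dose but before day 10 have no scheduled contact until about day 30, so the rhabdomyolysis inquiry has no planned occasion during their remaining dosing days

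*Protocol*

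**What the plan says.** Protocol section 2.10 sets two follow-up schedules. Inpatients are assessed daily from the medical record until they leave hospital or reach day 30. After an earlier discharge there is one further contact: "For participants discharged prior to 30 days-post randomization, a follow-up call will be performed at the ~30-day time point". That call asks whether the participant is alive, how they are functioning, what symptoms they have, and about major adverse events. The footnote to Figure 2 agrees that "inpatient mandatory data collection will occur until discharge or 30 days (whichever is shorter"). In Appendix 2 the only follow-up call shown for inpatients is the one at about 30 days.

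The second schedule covers participants randomized as outpatients and those who leave hospital within 24 hours of the first dose. For them, "participants will be called at approximately 5, 10, 15 and 30 days post-randomization".

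Treatment runs for 10 days according to the protocol summary and sections 2.1 and 2.5. The US part of Appendix 3 adds: "In all cases, the intended duration of randomized treatment will be for 10 days".

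On safety, section 8.2 states: "We will inquire about potential manifestations of rhabdomyolysis (particularly hemoglobinuria) in all data collection forms". It also says that study drug stops at once if rhabdomyolysis is suspected or confirmed. Section 2.7 lists stopping rules that apply at any time, including suspected rhabdomyolysis and red or brown urine. Section 2.8 asks outpatients to report newly started medication during the treatment period. Appendix 2 allows adverse event and withdrawal forms to be completed whenever needed.

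**The concern.** Scheduled contact follows enrolment status and the 24-hour discharge line, not whether the participant is still taking study drug. The 24-hour line matches the ranking rule for the primary endpoint in section 3, and no safety reason is given for it. Two inpatients discharged just inside and just outside 24 hours have nearly the same doses left, yet one is due four calls and the other is due one.

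Section 8.2 treats periodic laboratory monitoring as unnecessary for so short a course and promises instead that every data form will ask about rhabdomyolysis. For an inpatient sent home mid-course, no form is scheduled while drug is being taken.

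Two things are at stake. The first is whether the study would learn of a stopping symptom in time to act on it. The second is data quality. The SAP's Safety Analysis summarizes adverse events by type and severity in all subjects. Its Sensitivity Analyses plot non-adherence as cumulative events by arm, which needs dates. Protocol section 7.2 also plans an as-treated analysis.

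**Working it through.** No sample size, power or alpha figure bears on this point, and the plan states no figure to reproduce. The check compares the contact schedule with the dosing period.

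Inputs:
- Intended course: 10 days (summary, sections 2.1 and 2.5, Appendix 3).
- Last scheduled inpatient assessment: day of discharge, d (section 2.10, Figure 2 footnote, Appendix 2).
- Next scheduled contact after discharge: about day 30 (section 2.10, Appendix 2).
- Outpatient calls: about days 5, 10, 15 and 30 (section 2.10).
- Assumption: the first dose is given close to randomization, so both clocks start together.

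Formulas: dosing days left at discharge = 10 − d; days to the next scheduled contact = 30 − d. The last three columns show what the remaining outpatient calls would add. Dosing days left at an added call = 10 − call day, or 0 if the call is on day 10 or later.

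| Discharge day d | Dosing days left (10 − d) | Days to next contact (30 − d) | First added call | Dosing days left at that call | Calls added |
|---|---|---|---|---|---|
| 2 | 8 | 28 | about day 5 | 5 | 3 |
| 4 | 6 | 26 | about day 5 | 5 | 3 |
| 5 | 5 | 25 | about day 10 | 0 | 2 |
| 7 | 3 | 23 | about day 10 | 0 | 2 |
| 9 | 1 | 21 | about day 10 | 0 | 2 |
| 10 to 14 | 0 | 20 to 16 | about day 15 | 0 | 1 |

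Three results follow.

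1. For discharge on days 2 to 9, the number of scheduled contacts between discharge and the end of dosing is zero. The day-30 call comes 30 − 10 = 20 days after the last intended dose, too late to inform a stop.
2. Participants on the outpatient schedule have two calls within the course, at about days 5 and 10.
3. Extending those calls gives a contact with several doses left only for discharge on days 2 to 4. For discharge on days 5 to 9 the first added call falls at about the end of dosing. It still shortens the wait for contact, for example from 25 to 5 days for discharge on day 5.

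**The case against.** Much of the opposing case stands.

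**Event-driven routes remain.** A reader might infer that the stopping rules cannot operate for these participants. The documents do not support that. The rules apply at any time, adverse event forms can be opened whenever needed, and sites must pass on any rhabdomyolysis. A spontaneous report, a treating clinician or a readmission could trigger a stop. What is missing is a scheduled inquiry. The laboratory-based rules (eGFR, AST/ALT) are not part of this gap, because no on-treatment test is scheduled for anyone.

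**Some text is outside this review.** The consent pages were removed and only the US version of Appendix 3 is present. Instructions to report symptoms may exist there.

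**The absolute risk looks small.** Section 8.2 cites 3 rhabdomyolysis cases in more than 8 million active-arm patient-days of a long-term trial. Half of 700 is 350 participants; 350 × 8 unobserved days = 2,800 patient-days; 2,800 × 3 / 8,000,000 ≈ 0.001 expected cases. A 100-fold higher risk gives about 0.1. That population did not have COVID-19, but the figure argues against alarm.

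**The time-to-onset figure does not help.** Section 8.2 says that "the median duration of therapy prior to rhabdomyolysis was 17.5 days". A reader might infer substantial risk inside the unobserved window. The figure describes patients still on drug at onset, whereas dosing here ends at day 10, and a median of 17.5 days does not say how many cases arose within 10.

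**Undercounting is not shown.** A reader might conclude that safety counts will be too low. Nothing in the documents demonstrates that, and both blinded arms follow the same schedule. Section 2.10 also limits outpatient calls to major adverse events and lists no adherence item for anyone, so copying those calls unchanged would not fill the data gap.

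**Section 2.8 can be read more broadly.** Its use of outpatients may include discharged participants still on drug. The wording leaves this open.

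None of these points supplies a scheduled contact during the remaining dosing days.

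**Conclusion.** The gap is real but narrow. Inpatients discharged more than 24 hours after the first dose and before day 10 have no scheduled contact for the rest of the course and none until about day 30. For them the promised rhabdomyolysis inquiry and the symptom-based stopping rules have no planned detection route and rely on unscheduled reports. Post-discharge adverse events rest on one late recall call and are at risk of under-ascertainment. The timing of drug stopping has no scheduled collection before that call.

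The size runs from 8 dosing days and 28 contact-free days (discharge on day 2) to 1 and 21 (day 9). It rests on two assumptions: that the first dose is near randomization, and that dosing continues at home. The second is implied by the 10-day course, since nothing ends dosing at discharge, but it is not stated. The documents give no distribution of discharge days, so the number affected is unknown. The primary endpoint is not affected: its inpatient ventilation and oxygenation components end at discharge, and vital status is collected at about day 30. This is a cheap improvement to safety follow-up, not a threat to the trial's main result.

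**What to change.** 1. In section 2.10 and Appendix 2, give every inpatient discharged before day 15 whichever of the calls at about days 5, 10 and 15 remain, using the existing outpatient follow-up eCRF. Keep the day-30 call.
2. Record adverse events and study drug adherence, including the date of any stop, at those calls.
3. State whether the new-medication request in section 2.8 covers discharged inpatients still on study drug.
4. Reconcile section 8.2, which names hemoglobinuria, with section 2.7, which names red or brown urine as a possible sign of myoglobinuria. Do this without adding clinical triggers; the sponsor must decide which wording stands.

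The cost is a protocol and schedule amendment plus one to three short calls per early-discharged inpatient, made with an existing form and the same kind of staff. No visits or tests are added. For discharge on about days 5 to 9 the benefit is mainly better ascertainment; an earlier chance to stop drug arises mainly for discharge on days 2 to 4.

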### 3. ENDPOINTS

The **primary endpoint** of the trial will be a global rank score that ranks patient outcomes according to 5 factors: (1) time to death (ranked from shortest to longest, up to 30 days post-randomization), (2) the number of days supported by mechanical ventilation (invasive or non-invasive) or extracorporeal membrane oxygenation (until hospital discharge, up to 30 days post-randomization, ranked from longest to shortest); (3) The inspired concentration of oxygen/percent oxygen saturation ( $\text{FiO}_2/\text{SpO}_2$ ) ratio area under the curve (until hospital discharge, up to 30 days post-randomization, ranked from highest to lowest); (4) For participants enrolled as outpatients who are subsequently hospitalized, the number of days out of the hospital during the 30 day-period following randomization (ranked from lowest to highest); (5) For participants enrolled as outpatients who don't get hospitalized during the 30-day observation period, the modified Borg dyspnea scale (mean value of assessments at ~5, ~10 and ~15 days). Patients who are enrolled as inpatients but discharged within 24 hours of receiving the first dose of the study medication will be ranked similarly to outpatients.

The global rank score has several advantages compared to binary outcomes (e.g., all-cause death) or time-to-event outcomes (e.g., time to death). It incorporates information about each of the highest-priority events in COVID-19, but allows these events to be prioritized within a single endpoint. For instance, the principal outcome of interest is death, but even if there is no difference in rate of death, we would still be interested in a shorter duration of invasive respiratory support, a shorter duration of hospital admission with better oxygenation parameters, and so on. This maximizes study power and minimizes the number of participants that need to be enrolled in order to detect clinically-meaningful differences.

**Figure 2** demonstrates how participants will be ranked hierarchically according to their clinical course. All primary analyses will be performed on an intent-to-treat basis.

**Secondary endpoints** will include:

- (1) Number of days alive, out of the intensive care unit, free of mechanical ventilation (invasive and non-invasive), extracorporeal membrane oxygenation (ECMO) or maximal available respiratory support in the 30 days following randomization.
- (2) A seven-category ordinal scale consisting of the following categories: 1, not hospitalized with resumption of normal activities; 2, not hospitalized, but unable to resume normal activities; 3, hospitalized, not requiring supplemental oxygen; 4, hospitalized, requiring supplemental

[figure not shown]
oxygen; 5, hospitalized, requiring nasal high-flow oxygen therapy, noninvasive mechanical ventilation, or both; 6, hospitalized, requiring extracorporeal membrane oxygenation (ECMO), invasive mechanical ventilation, or both; and 7, death.

(3) A global rank score similar to the primary endpoint, but using a more comprehensive COVID-19 symptom scale instead of the dyspnea Borg scale (Appendix 1).

**Exploratory endpoints** will include:

- (1) All-cause death.
- (2) Number of days alive and out of the hospital during the 30 days following randomization.
- (3) A global rank score similar to the primary endpoint, but built only with factors 1-4.

